2.3.2.2 All Bleeds

In addition to treated bleeds, “all bleeds” will be analyzed as an additional endpoint. This definition comprises both treated and non-treated bleeds. In this definition, all bleeds are included, irrespective of treatment with coagulation factors, with the following exception: bleeds due to surgery/procedure are excluded from analysis—similar as in the analysis of treated bleeds.

The endpoint of “all bleeds” fulfills the adapted ISTH criteria, as described in the protocol and the 72-hour rule, in particular. This applies to the “all bleeds” definition as well. As “all bleeds” comprises treated and non-treated bleeds, the 72-hour rule will be implemented separately for the treated and non-treated bleeds.

For treated bleeds, the 72-hour rule is implemented exactly as defined for the “treated bleeds” endpoint (see Section 2.3.2.1).

For non-treated bleeds, the 72-hour rule is implemented by calculating a treatment-free period of 72 hours from the bleed itself. That is, a non-treated bleed is counted as a new bleed if it occurs more than 72 hours after the first sign of the preceding non-treated bleed or after the last treatment for a bleed.

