4.5.8 Bleed Definitions

Definition of a Bleed

For the purpose of the efficacy analyses, a standardized definition of bleed, adapted from criteria defined by the Subcommittee on Standards and Criteria, FVIII/FIX subcommittee of the International Society of Thrombosis and Hemostasis, and similar to that used in a recent clinical study, will be utilized in this study (Blanchette et al. 2014; Mahlangu et al. 2014).

- An event is considered a bleed if coagulation factors are administered to treat signs or symptoms of bleeding (e.g., pain, swelling, etc.). An additional definition of all reported bleeds (irrespective of treatment with coagulation factors) will be applied for a separate analysis.
- Bleeds starting from the first sign of bleed and ending 72 hours after the last treatment for the bleed, within which any symptoms of bleeding at the same location or injections are ≤ 72 hours apart, are considered the same bleed.
- Any injection to treat the bleed, taken > 72 hours after the preceding injection, is considered the first injection to treat a new bleed at the same location.
- Any bleed at a different location is considered a separate bleed regardless of time from last injection.

Definitions of Bleed Sites

- Target joints: defined as a major joint (e.g., hip, elbow, wrist, shoulder, knee, and ankle) into which repeated bleeds occur (frequency of ≥ 3 bleeds into the same joint over the last 24 weeks prior to study entry)
- Joint bleeds are defined as bleeds with bleed type “joint bleed” reported via the bleed/medication questionnaire with at least one of the following symptoms:
 - Increasing swelling or warmth of the skin over the joint
 - Increasing pain
 - Progressive loss of range of motion or difficulty in using the limb as compared with baseline
- Muscle bleeds (sites as per the bleed/medication questionnaire)
- Other (sites as per the bleed/medication questionnaire)

Definitions of Bleed Types

In addition, the assessment of a bleed will be separated into spontaneous bleeds, traumatic bleeds and bleeds related to procedure/surgery. Both spontaneous bleeds (i.e., the occurrence of hemorrhage where neither the patient nor a caregiver can identify a reason) and traumatic bleeds (i.e., hemorrhage occurring secondary to an event such as trauma, “strenuous” activity, or “overuse”) will be collected.

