2.3.2.1 Treated Bleed

A bleed is considered to be a “treated bleed” if it is directly followed (i.e., there is not an intervening bleed) by at least one hemophilia medication reported to be a “treatment for bleed” as specified in the BMQ, irrespective of the time between the treatment and the preceding bleed. A bleed and the first treatment thereafter and before a new bleed starts, are considered to be pairs (i.e., one treatment belongs to one bleed only), with the following exception: if multiple bleeds occur on the same calendar day, the subsequent treatment is considered to apply for each of these multiple bleeds.

Bleeds due to surgery/procedure are not included in the analysis. Only treatments that were recorded as “treatment for bleed” are included in the determination of a treated bleed. Note that a bleed can be treated with more than one treatment.

72-Hour Rule:

Two bleeds of the same type (e.g., “joint,” “muscle,” or “other”) and at the same anatomical location are counted as one bleed if the second bleed occurs within 72 hours from the last treatment for the first bleed. The last treatment is defined as the last treatment associated with the bleed before a new bleed occurs, either in the same or in a different location.

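### The SAP's 72-hour sentence for non-treated bleeds omits the same-type, same-location condition; coded literally, it would undercount the all-bleeds endpoint

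*SAP*

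**What the plan says.** Protocol 4.5.8 defines a bleed for the efficacy analyses as one treated with coagulation factors. It then adds a second endpoint: "An additional definition of all reported bleeds (irrespective of treatment with coagulation factors) will be applied for a separate analysis". Its merging rule concerns symptoms or injections at one location, and it closes with "Any bleed at a different location is considered a separate bleed regardless of time from last injection".

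SAP 2.3.2.1 carries this over for treated bleeds under the label of the 72-hour rule: "Two bleeds of the same type (e.g., “joint,” “muscle,” or “other”) and at the same anatomical location are counted as one bleed", provided the second falls within 72 hours of the last treatment for the first.

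SAP 2.3.2.2 covers all bleeds. It says the endpoint "fulfills the adapted ISTH criteria, as described in the protocol and the 72-hour rule, in particular", and that the rule will be implemented separately for treated and non-treated bleeds. Treated bleeds follow 2.3.2.1 exactly. For the others, "For non-treated bleeds, the 72-hour rule is implemented by calculating a treatment-free period of 72 hours from the bleed itself". The next sentence spells this out: "a non-treated bleed is counted as a new bleed if it occurs more than 72 hours after the first sign of the preceding non-treated bleed", followed by a second limb, "or after the last treatment for a bleed". Neither limb mentions type or location.

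**The concern.** The sentence that gives the counting rule for non-treated bleeds lacks the matching condition found everywhere else. A programmer who codes it as it stands would compare each untreated bleed with the previous untreated bleed at any site. An untreated left-knee bleed on Monday and an untreated right-elbow bleed on Tuesday would count once. Had both been treated, they would count twice.

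All bleeds is a named efficacy objective (protocol 2.2.1, SAP 2.3.2), and SAP 4.5.3 reports its ABR with a 95% CI in each pre-specified subgroup. An error here has one direction: relative to the location-specific rule, it can only lower the count. It bears most on patients who bleed often or at several sites at once. The pairing rule in SAP 2.3.2.1 adds to the exposure. If the knee bleeds on Monday, the elbow on Tuesday and the ankle on Wednesday, with one infusion after the ankle, then the knee and elbow bleeds are classed as non-treated and fall under this sentence.

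**Working it through.** The documents give no all-bleeds rate or other figure that depends on this rule, so there is nothing to reproduce. The check has two parts: applying the two readings to a sequence, and sizing the gap under stated assumptions.

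**1. The conditions side by side**

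| Source | Clock starts at | Same type required | Same location required |
|---|---|---|---|
| Protocol 4.5.8 | last treatment/injection | not stated | yes |
| SAP 2.3.2.1, treated | last treatment | yes | yes |
| SAP 2.3.2.2, non-treated | first sign of preceding non-treated bleed, or last treatment for a bleed | not stated | not stated |

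**2. A worked sequence**, all untreated, with no treatment on record, so only the first limb operates: left knee at 0 h, right elbow at 24 h, left ankle at 60 h, left knee at 150 h.

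- Literal sentence: the gaps are 24, 36 and 90 h. Only the last exceeds 72, so the count is 2. The count is also 2 if the preceding bleed means the last one counted rather than the last one reported.
- With a same-location condition: elbow and ankle are new sites, and the second knee bleed comes 150 h after the first. The count is 4.

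**3. Size under literal coding of the first limb.** Assumptions, none of them document figures: untreated bleeds arrive independently at λ per patient-year, spread evenly over 12 sites (the six major joints listed in protocol 4.5.8, two sides each).

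Share of untreated bleeds lost ≈ (1 − exp(−3λ/365.25)) × 11/12

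- λ = 2: (1 − exp(−0.01643)) × 11/12 = 1.6% × 11/12 = 1.5%
- λ = 5: (1 − exp(−0.04107)) × 11/12 = 4.0% × 11/12 = 3.7%

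A simulation of 40 patients followed for 24 weeks, comparing the literal rule with the same-location rule, also gave 3.7% at λ = 5, and 0.8% at λ = 1 and 2.1% at λ = 3.

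In absolute terms, 40 patients × 168 days / 365.25 = 18.4 patient-years. At λ = 2 that is about 37 untreated bleeds and a loss of about half a bleed (37 × 1.5%). At λ = 5 it is about 92 and a loss of about 3 (92 × 3.7%).

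**4. Clustering.** The same simulation, with a second site involved within 72 h in an assumed share of episodes:

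| λ per year | 10% of episodes | 25% of episodes |
|---|---|---|
| 1 | 10.0% | 20.9% |
| 3 | 10.8% | 21.9% |
| 5 | 12.3% | 22.9% |

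**5. Dilution.** These are shares of untreated bleeds. If untreated bleeds are a fraction u of all bleeds and the loss is L, the all-bleeds ABR falls by u × L, which cannot exceed L.

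**6. The second limb.** It does not say whether the treatment must be for a bleed at the same site. It also joins the limbs with 'or'. If either limb suffices, an untreated bleed long after any treatment is always new, even at the same site an hour after another untreated bleed. If both must hold, treatment of a bleed elsewhere can absorb an untreated one. The text does not decide between these.

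**The case against.** The best defence is that the location condition enters by reference. SAP 2.3.2.2 ties the endpoint to the protocol's criteria and to the 72-hour rule, which SAP 2.3.2.1 defines with type and location. On that view the disputed sentence only says where the clock starts when there is no treatment to start it. Read so, different sites stay separate and nothing is lost. This stands as a possible reading, and no programming specification is available to settle the matter. It does not remove the defect. The section declares a separate implementation for non-treated bleeds, reserves the exact 2.3.2.1 rule for treated ones, and then writes out a rule that looks complete. Two competent programmers could derive different counts from it.

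Three further points stand:

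- A reader might infer that an untreated ankle bleed two days after an infusion for a shoulder bleed is never counted. That requires both limbs to hold. If either suffices, the bleed counts whenever the last untreated bleed was more than 72 hours earlier.
- A reader might extend the independence formula to 10 or 20 untreated bleeds a year, giving 7.2% and 13.9%. Nothing in the documents supports such rates on prophylaxis.
- All bleeds is an additional endpoint in a descriptive study without hypothesis tests, so no decision threshold turns on it. Bleeds are also listed by patient (SAP 4.5.1), which would help to expose merging.

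**Conclusion.** The sentence is wrong as written. It omits a condition that SAP 2.3.2.1 states for treated bleeds, conflicts with the protocol's treatment of different locations, and so contradicts its own section's claim to follow the protocol's criteria. It is also unclear whether the treatment limb is site-specific and whether both limbs must hold.

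The undercount is conditional on literal coding. Under independence over 12 sites it is about 1.5% of untreated bleeds at 2 per patient-year and 3.7% at 5. It is larger if multi-site episodes cluster, smaller in the all-bleeds ABR, and zero if the location condition is read in. The bleed rates, number of sites and clustering shares are all assumptions.

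Two stronger conclusions are tempting and not supported. One is that the plan definitely merges different sites, so that an undercount is established; the cross-references in SAP 2.3.2.2 prevent that. The other is that the main efficacy result is biased; SAP 2.3.1 counts only treated bleeds in the primary analysis, and this sentence does not touch them.

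**What to change.** Reword the non-treated rule in SAP 2.3.2.2 along these lines:

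> A non-treated bleed is merged with an earlier bleed only if it is of the same type and at the same anatomical location, and starts within 72 hours of the first sign of the preceding non-treated bleed at that location or of the last treatment for a bleed at that location. A non-treated bleed at a different location is always counted separately.

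Writing the rule as a condition for merging also settles the 'or': either clock is enough to merge, and only at the same site.

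The cost is one sentence and one matching key in the derivation program. No new data are needed, because the bleed and medication questionnaire already records type and location (SAP 2.2.1). The all-bleeds ABR may become slightly higher. If the program already applies the location condition to both limbs, the edit changes no result and brings the SAP into line with protocol 4.5.8.

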2.3.2.3 Treated Spontaneous Bleeds

In the analysis of spontaneous bleeds, only treated bleeds that fulfill the 72-hour rule are included.

Bleeds are classified as “spontaneous” if there is no other known contributing factor such as trauma or procedure/surgery.

2.3.2.4 Treated Joint Bleeds

In the analysis of joint bleeds, only treated bleeds that fulfill the 72-hour rule are included. Bleeds due to procedure/surgery are again excluded.

Joint bleeds are defined as bleeds where the bleed type is “joint” as reported in the BMQ and is reported with at least one of the following symptoms: increasing swelling or warmth of the skin over the joint and/or increasing pain, decreased range of motion, or difficulty in using the joint compared with baseline.

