- Spontaneous bleeds: Bleeds should be classified as spontaneous if a patient records a bleed when there is no known contributing factor such as definite trauma, antecedent “strenuous” activity or “overuse.” The determination of what constitutes “strenuous” or “overuse” will be at the discretion of the patient. For example, light jogging may be considered “non-strenuous” while sprinting may be considered “strenuous,” lifting of weights for a short period of time may be considered “moderate use” while repetitive weightlifting may be considered “overuse.”
- Traumatic bleeds: Bleeds should be classified as traumatic if a patient records a bleed when there is a known or believed reason for the bleed. For example, if a patient were to exercise “strenuously” and then have a bleed in the absence of any obvious injury, the bleed would be recorded as a traumatic bleed because, although no injury occurred, there was antecedent “strenuous” activity. Bleeds subsequent to injuries would certainly be classified as traumatic.
- Bleeds related to procedure/surgery: such as hematomas resulting from any surgeries or invasive procedures (e.g., tooth extractions, venipuncture, or SC drug administrations) or invasive diagnostic procedures (e.g., lumbar puncture, arterial blood gas determination, or any endoscopy with biopsy, etc.) would not be counted as bleeds. Bleeds related to procedure/surgery are not associated with any trauma except procedure/surgery-induced trauma.

Patients (or their legally authorized representative) will complete a bleed/medication questionnaire weekly and whenever a bleed occurs via an electronic, handheld device. For each bleeding episode, they will provide information on the above topics as well as on the medication used to treat the bleed. Hemophilia medications that were taken will also be collected through the bleed/medication questionnaire. If the electronic, handheld device is not available, a paper questionnaire might be used. Investigators will review the bleed and bleed medication data as per the schedule of assessments (see [Appendix 1](#)) and have the option to correct or complete these in agreement with the patient via a Data Request Form process or via a Web-based portal, once implemented. The Sponsor will have view-access only but will do a review of the bleed and bleed medication data as per the Medical Data Review Plan.

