2.2 COLLECTION OF PATIENT-REPORTED DATA

2.2.1 Collection of Bleed and Medication Data

Bleed and medication data are collected through a bleed and medication questionnaire (BMQ), which was developed by the Sponsor given that no standard questionnaire for collection of this data was available. The BMQ was developed as a patient-reported measure of bleeding episodes (including cause, type, location, and symptoms of bleeds) and hemophilia-related medication use. This questionnaire was initially used in the non-interventional study (NIS; BH29768), patients with inhibitors study (BH29884), and later in the studies for pediatric patients (Study BH29992) and the non-inhibitor patients (Study BH30071).

To capture bleed data, emicizumab use, and other hemophilia medication use during study treatment, patients will complete the BMQ on a handheld device that will be provided to them during the Week 1 visit at the study site. This device will remain with the patient for the duration of the study to enter bleed and medication data weekly at a minimum. In case a patient did not experience any bleeds or administer any treatments for a week, the patient is asked to log into the device and fill in the questionnaire to confirm this. These weekly entries, in addition to the bleeds and medication entries can also be used to assess compliance. Of note, the patient is able to enter bleeds and medications for the past 8 days, including the day the entries are made. This retrospective data entry window was considered acceptable in terms of recall bias and was added in order to optimize the completeness of data collection.

Patients who withdraw from emicizumab treatment will continue to record bleeds and hemophilia medication administration until they complete the safety follow-up visit.

The patient is able to edit and delete bleeds and medications for 24 hours after they are entered. Furthermore, the investigator and patient are instructed to review the data together at every clinic visit. If the patient has been unable to enter data for any reason, the investigator is able to do so using a data clarification request (Data Change Request [DCR]; not subject to the previous 8-day data entry window). Note, the symptoms of joint and muscle bleeds are not collected in this case because the patient may not be

able to reliably remember them. In addition, the investigator is able to request a change be made to the vendor's database by submitting a DCR.

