Furthermore, the Sponsor's data manager and Medical Monitor review the patient entered data for clear inconsistencies against data collected on the electronic Case Report Form (eCRF) or to identify obvious data points to be clarified (e.g., missing entry of the weekly emicizumab injection). These requests are sent to the investigator, who reviews them with the patient and may enter the data via the site data entry system or request a change to be made in the vendor's database via a DCR, if necessary.

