2.3.2.5 Treated Target Joint Bleeds

Target joints are joints into which repeated bleeds occur (i.e., ≥ 3 bleeds into the same joint over the last 24 weeks prior to study entry). The target joints prior to study entry are identified through the eCRF. The bleeds in target joints during the efficacy period are defined by first selecting the bleeds that fulfill the definition of a treated joint bleed and then counting how many of these occurred in a target joint as defined prior to study entry. The locations to be taken into account are shoulder, elbow, wrist, fingers/thumb, hip, knee, ankle, sole/heel, and toes. Left and right sides of the same joint type are considered to be separate joints.

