4.9 MISSING DATA

On the electronic, handheld device, it is not possible to leave questions unanswered or to enter partial data. Therefore, the data for bleed-related endpoints coming from the electronic, handheld device are complete.

In the site data entry system (Gather), it is possible to leave the time of a treatment or a bleed blank because the patient might not be able to reliably remember these.

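### Joint bleeds entered only by the investigator carry no symptom data, so read literally they drop out of the joint and target-joint bleed rates; the SAP should flag, count and test them

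*SAP*

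**What the plan says.** SAP 2.2.1 has patients record bleeds on a handheld device, with an 8-day look-back. It also provides a fallback: "If the patient has been unable to enter data for any reason, the investigator is able to do so using a data clarification request". That fallback is not bound by the 8-day window. For bleeds entered this way the same section states: "Note, the symptoms of joint and muscle bleeds are not collected in this case". The reason given is doubtful recall, not absence of symptoms.

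SAP 2.3.2.4 takes treated bleeds that satisfy the 72-hour rule and counts as joint bleeds those of type joint "as reported in the BMQ and is reported with at least one of the following symptoms". Protocol 4.5.8 sets the same condition: the bleed type must be "reported via the bleed/medication questionnaire with at least one of the following symptoms". SAP 2.3.2.5 obtains target-joint bleeds by "first selecting the bleeds that fulfill the definition of a treated joint bleed", so it inherits the condition.

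SAP 4.9 treats the handheld data as complete. For the site data entry system it says only that "it is possible to leave the time of a treatment or a bleed blank". It gives no rule for symptoms that were not collected. SAP 2.3.1 defines the bleed rate over the efficacy period and removes no days on account of entry route.

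**The concern.** One section says that a piece of information is not gathered on a certain route; another makes that information a condition for counting. Nothing links the two, so uncollected symptoms are handled as if there were none.

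Joint bleeds and target-joint bleeds over time are named efficacy objectives (protocol 2.2.1, SAP 2.3.2). The study tests no hypothesis, so these estimates are themselves the result. A loss that runs in one direction only, and that favours the drug, should at least be visible to the reader.

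The fallback has a real use. Appendix 1 of the protocol schedules the investigator's bleed review every 4 weeks from Week 5, while the patient can enter only the past 8 days. A bleed first mentioned at review may have fallen on any of up to 28 − 8 = 20 days that the patient can no longer enter.

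**Working it through.** The plan states no figure to reproduce. The check is a reading of the rules, followed by arithmetic for scale.

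**Tracing the rule**

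1. A treated bleed of type joint is entered only by data clarification request. No symptoms are recorded (SAP 2.2.1).
2. It can still be a treated bleed, because SAP 2.3.2.1 asks for a treatment and not for symptoms. It also remains eligible for the spontaneous-bleed and all-bleed counts.
3. It fails the symptom condition of SAP 2.3.2.4, and hence SAP 2.3.2.5.
4. Its days remain in the denominator (SAP 2.3.1). Steps 3 and 4 can lower the two rates but cannot raise them.

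**Proportional loss**

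Let *N* be the treated type-joint bleeds after the 72-hour rule, *f* the share entered only by the investigator, *p* the fraction of those that were in truth symptomatic, and *q* the symptomatic fraction of device-entered ones. None of these is in the documents; all values below are assumptions.

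- Symptomatic joint bleeds: N[(1 − f)q + fp]
- Counted joint bleeds: N(1 − f)q
- Loss = fp / [(1 − f)q + fp]

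When p = q this reduces to f.

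| f | p = q | p = 0.5, q = 1 | p = 1, q = 0.8 |
|---|---|---|---|
| 5% | 5% | 0.025/0.975 = 2.6% | 0.05/0.81 = 6.2% |
| 10% | 10% | 0.05/0.95 = 5.3% | 0.10/0.82 = 12.2% |
| 20% | 20% | 0.10/0.90 = 11.1% | 0.20/0.84 = 23.8% |

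The last column shows that f is not an upper limit: the loss exceeds f whenever p is larger than q.

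**Effect of one lost bleed on the crude rate (bleeds per patient-year)**

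Inputs: 40 expansion patients (SAP 2) and 24 weeks, or 168 days, as the time each non-withdrawn patient has completed at the primary analysis (SAP 2.5). The longer means are assumed, because the efficacy period runs to the clinical cutoff.

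- 24 weeks: 40 × 168/365.25 = 18.40 patient-years; 1/18.40 = 0.054
- 36 weeks: 40 × 252/365.25 = 27.60; 1/27.60 = 0.036
- 48 weeks: 40 × 336/365.25 = 36.80; 1/36.80 = 0.027

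**Example**

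Assume 20 type-joint bleeds in 18.40 patient-years, all symptomatic, with f = 10%. The plan counts 18: 18/18.40 = 0.98, against 20/18.40 = 1.09.

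**The case against.** **Scale.** The route is a fallback. Weekly confirmation even without bleeds, the 8-day look-back and joint review at every clinic visit (SAP 2.2.1) all keep f small, possibly zero. In the example above, an exact Poisson 95% interval for 20 bleeds in 18.40 patient-years is about 0.66 to 1.68, so a move from 1.09 to 0.98 lies well inside it. This stands, and it is why the severity is low. It does not remove the point, since the shift is systematic and sampling error is not.

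**The definition is defensible.** A symptom-confirmed joint bleed is what protocol 4.5.8 asks for. This also stands, and the main analysis should keep it.

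**The loss is not hidden.** SAP 4.5.1 plans summaries and patient listings of bleeds by type and location. Setting treated type-joint bleeds against the joint-bleed count bounds the number excluded, so a reader who infers that the exclusions would be invisible goes too far. What the listings do not separate is symptoms not collected from no symptom reported.

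**Practice may differ from the text.** Protocol 4.5.8 allows investigators to correct or complete bleed data in agreement with the patient. That might let symptoms be filled in, but SAP 2.2.1 says the opposite for this route.

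**Stronger readings that the documents do not support:**

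- That every site-entered or paper entry lacks symptoms. After a sponsor query the investigator "may enter the data via the site data entry system", and protocol 4.5.8 adds: "If the electronic, handheld device is not available, a paper questionnaire might be used". Neither text says whether symptoms are collected there.
- That investigator corrections are affected. An entry that the patient made with symptoms keeps them.
- That a bleed merging with another under the 72-hour rule costs nothing. If the entry without symptoms comes first, the SAP does not say whether the merged bleed takes the symptoms of the later one.

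**Conclusion.** The point holds for one route: treated type-joint bleeds entered only by data clarification request because the patient could not enter them. As written, they cannot count in the joint or target-joint rate, and both rates can only be lowered.

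The size is unknown and may be nil. The proportional loss equals f if investigator-entered and device-entered type-joint bleeds are equally often symptomatic, and is smaller or larger otherwise. The 0.054 per lost bleed assumes 40 patients at 24 weeks each and shrinks with longer follow-up.

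A reader might infer that the trial's main efficacy result is biased. The documents do not support that: the key objective rests on treated bleeds, which carry no symptom condition, and the same is true of spontaneous and all bleeds. Nor do they support a claim that the joint rates are materially understated, since they give no value for f. This is a low-severity gap in two descriptive endpoints.

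**What to change.** Keep the symptom-confirmed definition of protocol 4.5.8 as the main analysis. Add to SAP 2.3.2.4, and carry into 2.3.2.5:

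- Treated bleeds of type joint whose symptoms were not collected because of the entry route are flagged, and their number is reported.
- A pre-specified sensitivity row for the joint and target-joint annualized rates counts these bleeds on bleed type alone, after the 72-hour rule.
- When two entries merge under the 72-hour rule, the text states whether the merged bleed takes the symptoms of either entry.

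So that the flag can be programmed, state in SAP 2.2.1 which entry routes (data clarification request, site data entry system, paper) collect symptoms.

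The cost is one flag, one count and one extra row in two tables, with no change to the protocol definition. The downside is that the sensitivity row may include a few bleeds without true joint symptoms. If the route was hardly used, the count will show it. The same rule would serve the updates and the final analysis foreseen in SAP 2.5.
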